4.3.2. Other Safety Endpoints

Clinical laboratory test, physical examination, 12-lead ECG, vital sign assessments will be collected and analyzed to evaluate the safety of MBS-COV.

Laboratory evaluation

Clinical Laboratory Assessments are listed below:

| | |
|------------------|---|
| Biochemistry | Total bilirubin (mg/dL), Alkaline Phosphatase (ALP) (U/L), Aspartate Aminotransferase (AST) (or SGOT) (U/L), Alanine Aminotransferase (ALT) (or SGPT) (U/L), Total Protein (g/dL), Albumin (g/dL), Lactate Dehydrogenase (LDH) (U/L), Amylase (U/L), Lipase (U/L), Serum creatinine (mg/dL), eGFR(ml/min/1.73 m ²), Sodium (mEq/L), Potassium (mEq/L), Chloride (mEq/L), Calcium (mg/dL), Bicarbonate (mEq/L), Glucose, Random (mg/dL), Creatine kinase (U/L), Triglyceride (TG) (mg/dL), Total Cholesteriol (TC) (mg/dL) |
| Hematology | Hemoglobin (g/dL), Hematocrit (%), RBC/Erythrocytes (10 ¹² /L), WBC/Leukocytes (10 ⁶ /L), Absolute Neutrophil Count (10 ⁶ /L), Platelets (10 ⁹ /L), Neutrophils (%), Lymphocytes (%), Monocytes (%), Eosinophils (%), Basophils (%) |
| Coagulation test | Prothrombin time (PT), Activated partial thromboplastin time (APTT), Thrombin time (TT), Fibrinogen (FIB) |
| Urinalysis | pH, Specimen Appearance, Color, Specific Gravity, Ketones, Bilirubin, Occult Blood, Glucose, Protein, Nitrite, Urobilinogen (mg/dL), Leukocyte, Esterase |

Besides, pregnancy test will be conducted in serum. A positive urine pregnancy test will be confirmed with a serum pregnancy test.

Results of Clinical Laboratory Assessments at each scheduled visit will be recorded on the CRF.

Physical examination

The physical examination will include routine examinations for the following:

- Constitutional/General Appearance
- Head, Ears, Eyes, Nose, Throat (HEENT)
- Neurologic

- Chest (including heart and lung)
- Abdomen
- Musculoskeletal and Extremities
- Dermatologic
- Lymphatic
- Psychiatric

Any findings made during the physical examination must be noted regardless of whether they are part of the subject's medical history.

Results at each scheduled visit will be recorded on the CRF.

12-lead ECG

12-lead ECG will include ventricular rate, PR interval, QRS interval, QT interval, and QTc interval and clinical overall evaluation.

Results at each scheduled visit will be recorded on the CRF.

Vital sign

The following vital signs will include Systolic and Diastolic Blood Pressure, Pulse, Respiratory Rate, Oral Temperature and clinical overall evaluation.

Results at each scheduled visit will be recorded on the CRF.

Spirometry assessment

Spirometry assessment will include FEV1%, FEV1/FVC, PEF.

Results at each scheduled visit will be recorded on the CRF.

4.3.3. Demographics and Baseline Characteristics

Subjects' age (in years, at time of signing informed consent), gender, race, ethnicity, height, weight, and BMI will be recorded on CRF.

A medical history will be recorded on the CRF and will include:

- All ongoing medical conditions
- All previously resolved medical conditions that are relevant in the judgment of the Investigator
- Any prior medical conditions that have resolved within the last year

Events that emerge prior to the first treatment will be recorded in the medical history. Medical history term, duration, and status will be recorded on the CRF

4.3.4. Concomitant Medication and Procedure

All medications and therapies administered or taken by the participant beginning 14 days prior to Screening Visit and throughout the study will be recorded on the CRF. Participants must be questioned at each study visit concerning any new medications or changes in current medications including over-the-counter medication and topical medication.

For each medication and non-study treatment, the following will be documented:

- Medication/treatment name (generic name may be used if trade name is unknown)
- Dose, unit, and frequency of dosing (individual dosages, not total daily dose).
- Route of dosing
- Indication for use
- The start date
- The stop date (if medication/therapy is not ongoing).

4.3.5. Protocol Deviations

A protocol deviation is any noncompliance with the protocol or study procedures detailed in the laboratory or pharmacy manuals. The noncompliance may have been the result of action by the PI, site staff, or subject.

4.4. Study PK Endpoint

Refer to separate PK statistical analysis plan.

5. Statistical hypothesis

No formal statistical hypothesis for this Phase I study.

6. Analysis Datasets

The following datasets for analysis will be used in this study:

- **Full Analysis Set (FAS):** FAS includes all randomized participants. This analysis set will be used to analyze the disposition, demographic and baseline characteristics of the subjects.
- **Safety Analysis Set (SS):** SS includes all the participants who receive the study drug at least once. This population will be used for the analysis of safety parameters.

- **Pharmacokinetic Concentration Analysis Set (PKCS):** PKCS includes all randomized participants who receive at least one dose of the study drug and have at least plasma concentration. The PKCS will be used for PK concentration analysis.
- **Pharmacokinetic Parameter Analysis Set (PKPS):** PKPS includes all randomized participants who receive at least one dose of the study drug with no major protocol violations or protocol deviations that have a significant impact on PK parameters (C_{max} , AUC, etc.), and have at least one analyzable PK parameter. The PKPS will be used for PK parameters analysis.
- **Immunogenicity Set (IS):** The IS includes all randomized participants who receive at least one dose of the study drug, and have at least one ADA concentration. The IS will be used for immunogenicity analysis.

Safety analysis will be based on the safety analysis set. The division of the analysis population will be determined before database lock.

7. Statistical Methods

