The SRC will review the PK data (if applicable) and safety trends of available information 7-day post treatment period of Cohort A1 and A2 (or if study stops prematurely due to safety reasons), to start part B of the study. The starting dose of Part B will be determined by SRC.

Figure 3-1: Dose Escalation Scheme

Blood Sample Collection for the PK study:

- SAD cohorts A1 to A3:** For the single dose on day 1, blood samples will be collected before dosing, and afterwards at 5 min (± 1 min), 15 min (± 2 min), 0.5 h (± 5 min), 1 h (± 5 min), 2 h (± 5 min), 4 h (± 5 min), 8 h (± 10 min), 10 h (± 10 min), 24 h (± 10 min) and 48 h (± 10 min) (Total 11 samples) after dosing.
- MAD cohort B1 and B2:** Blood samples will be collected on Day 1 and Day 7 before dosing, and afterwards at 5 min (± 1 min), 15min (± 2 min), 0.5 h (± 5 min), 1 h (± 5 min), 2 h (± 5 min), 4 h (± 5 min), 8 h (± 10 min), 10 h (± 10 min) on Day 1; and at 5 min (± 1 min), 15min (± 2 min), 0.5 h (± 5 min), 1 h (± 5 min), 2 h (± 5 min), 4 h (± 5 min), 8 h (± 10 min) on Day 7.

10 min), 10 h (\pm 10 min), 24 h (\pm 10 min) and 48 h (\pm 10 min) after dosing on Day 7; and before dosing on Day 2 to Day 6 (Total 25 samples). The detailed study schedule and assessments in each visit are provided in [Section 4](#) of the protocol.

Blood Sample Collection for the immunogenicity study:

- Blood Sample will be collected on Day 1 before dosing, Day 14 and Day 28 for SAD and MAD cohorts, and the analysis will be performed when analytic method is well-established.

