5.2.2. Data Collected from Withdrawn Participants

In the case of early termination, assessments listed in [Section 4.2.4](#) and [Section 4.3.6](#) will be completed when possible.

Every attempt should be made to collect follow-up information. The reason for withdrawal from the study will be recorded in the source documents and on the appropriate page of the CRF.

Before a participant is identified as lost-to-follow up, the site should make all reasonable efforts to contact the participant. These attempts must be documented and should include at a minimum one phone call and one certified letter.

In the event that a participant is withdrawn from the study at any time due to an AE or SAE, the procedures stated in [Section 9.2](#) (AE) or [Section 9.4](#) (SAE) must be followed.

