8.7.1.5. Immunogenicity Set (IS)

IS includes all randomized participants who receive at least one dose of the study drug, and have at least one ADA concentration. The IS will be used for immunogenicity analysis.

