4.1.2. Secondary Outcome Measures

The secondary outcome measures in this study are:

Pharmacokinetic Outcome Measures:

- Maximum observed plasma drug concentration (C_{max})
- Apparent terminal elimination half-life ($t_{1/2}$)
- Time to maximum observed plasma drug concentration (T_{max})
- Area under the plasma drug concentration-time curve (AUC) from time 0 to the time of the last quantifiable concentration (T_{last}) (AUC_{0-t})
- AUC from time 0 to infinity ($AUC_{0-\infty}$)
- Apparent plasma clearance (CL/F)

Immunogenicity Outcome Measure:

- Occurrence of anti MBS-COV antibody after administration of MBS-COV

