7.1. General Statistical Consideration

If no other specified, SAS® (Version 9.4 or above) statistical software will be used for all statistical calculation and all analyses of safety part.

All summaries will be provided by treatment group for both study parts. Continuous variables will be summarized using descriptive statistics including number of observations (n), mean, standard deviation, median (med), minimum (min) and maximum (max). Categorical variables will be summarized using frequency and percentages.

For laboratory examination, keep 2 decimal places for mean, minimum, median, and maximum, 3 decimals for standard deviation. For percentage, keep 1 decimal place.

If no other specified, baseline of safety analysis is defined as the last effective assessment record before first treatment dosing.

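### The Immunogenicity Set admits dosed participants who have only a pre-dose ADA sample, so a percentage based on it can include people in whom post-dose antibody could not be observed

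*SAP*

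**What the plan says.** Both documents define the Immunogenicity Set in the same terms. The SAP, Section 6, has: "The IS includes all randomized participants who receive at least one dose of the study drug, and have at least one ADA concentration". Protocol 8.7.1.5 has: "IS includes all randomized participants who receive at least one dose of the study drug, and have at least one ADA concentration". Neither says that the ADA result must come from a sample taken after dosing.

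This is the only population named for the purpose: "The IS will be used for immunogenicity analysis" (SAP Section 6). The outcome, listed for both parts, is "Occurrence of anti MBS-COV antibody after administration of MBS-COV" (SAP 4.1.2 and 4.2.2). The sampling plan in protocol 3.1 is: "Blood Sample will be collected on Day 1 before dosing, Day 14 and Day 28 for SAD and MAD cohorts". There is thus one sample before dosing and two after.

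For participants who leave early, protocol 5.2.2 begins "In the case of early termination, assessments listed in" and points to Sections 4.2.4 and 4.3.6. Neither section lists an ADA sample.

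The SAP has no section on the immunogenicity analysis. Its baseline rule in 7.1 is framed for safety: "If no other specified, baseline of safety analysis is defined as the last effective assessment record before first treatment dosing".

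**The concern.** An outcome that can be seen only on Day 14 or Day 28 should be summarised over participants who have a result on at least one of those days. The set as defined also takes in anyone who was dosed and has nothing but the Day 1 pre-dose sample. The protocol's own early-termination procedure can produce such a participant: someone who withdraws before Day 14 and does not return has no post-dose ADA sample.

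Immunogenicity is a stated secondary objective, and active groups have 6 or 8 people. In a table by treatment group, one unobservable participant changes the percentage visibly.

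A second, smaller gap concerns the numerator. The Day 1 sample is scheduled for everyone, but no rule says how it is used, so the plan does not separate antibody present before dosing from antibody that appears afterwards.

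**Working it through.** **Inputs from the documents**

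- Allocation (protocol 8.4): three Part A cohorts of 6 active and 2 placebo, and two Part B cohorts of 8 active and 2 placebo. The stated total is reproduced: 3×8 + 2×10 = 44. Active: 3×6 + 2×8 = 34. Placebo: 5×2 = 10.
- ADA samples: Day 1 pre-dose, Day 14, Day 28. Only the last two can show the outcome.
- The documents give no expected ADA rate, no dropout rate and no prevalence of pre-existing ADA, so there is no ADA figure in the plan to reproduce.

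**Assumed for illustration**

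- x = 1 participant positive after dosing.
- m = 0, 1 or 2 set members with a pre-dose sample only.
- d = 2% to 15% probability that a dosed participant has no Day 14 and no Day 28 sample, independently of the others.

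**Step 1. Denominator.** With n active participants in the set, the rate on the set is x/n and the rate among those observable is x/(n − m). The first is the second multiplied by (n − m)/n.

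| Active group | m | On the set, x/n | Observable, x/(n − m) |
|---|---|---|---|
| 6 (Part A cohort) | 1 | 1/6 = 16.7% | 1/5 = 20.0% |
| 6 | 2 | 1/6 = 16.7% | 1/4 = 25.0% |
| 8 (Part B cohort) | 1 | 1/8 = 12.5% | 1/7 = 14.3% |
| 8 | 2 | 1/8 = 12.5% | 1/6 = 16.7% |
| 34 (all active) | 1 | 1/34 = 2.9% | 1/33 = 3.0% |
| 34 | 2 | 1/34 = 2.9% | 1/32 = 3.1% |

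With m = 0 the two columns agree.

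**Step 2. How easily m ≥ 1 arises.** The chance of at least one such participant is 1 − (1 − d)^n. For d from 2% to 15%:

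- n = 6: 11% to 62%
- n = 8: 15% to 73%
- n = 34: 50% to 99.6%

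These figures depend wholly on the assumed d.

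**Step 3. Numerator.** If one participant reactive before dosing were counted as an occurrence, the rate would rise by 1/n: 16.7 points for n = 6, 12.5 points for n = 8 and 2.9 points for n = 34. The documents do not say that such a participant is counted.

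**Step 4. Does other text repair the definition?**

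- Protocol 8.7.2 leaves missing data to the SAP. SAP 7.2.1 rules out imputation for the safety part only.
- The SAP 7.1 baseline rule is for safety.
- The separate plan cited in SAP 4.4, 7.2.3 and 7.5 is named for PK only.
- SAP Section 6 leaves the final division of populations to be settled before database lock, but gives no further criterion for this set.

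None of these adds a post-dose condition.

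**The case against.** The strongest reply is that a set definition says who is a member, not how each member is scored. A reader might infer that a participant without a post-dose sample counts as ADA-negative, so that the plan as written biases incidence downwards. No text says so. The SAP writes no incidence formula, and the nearest sentence, in 7.2.1, allows missing categorical data to be shown as missing, although its reach beyond safety is unclear. This part of the reply stands: the dilution follows only if the set is used as the percentage denominator. That is the natural use of the only set named, given that SAP 7.1 summarises categorical data by frequency and percentage, but it is not stated.

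A reader might likewise infer that pre-dose reactivity counts as an occurrence and biases incidence upwards. The documents do not support that either. They are silent on how pre-dose reactivity is handled, and the outcome is worded as occurring after administration.

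The size is also hypothetical. A participant must miss both Day 14 and Day 28 to have no post-dose sample. The protocol works against this: it keeps following people who stop treatment where it can (5.2.1), asks sites to make up missed visits (4.5) and seeks follow-up data after withdrawal (5.2.2). Part B participants stay in the clinic until Day 9. The measure is descriptive, no hypothesis is tested, and the synopsis promises participant listings in which each ADA series could be read. All of this limits the consequence. None of it makes a pre-dose sample informative about post-dose antibody, or gives a reason to keep the looser wording.

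**Conclusion.** The point holds in a limited form. Both documents state a membership rule that a pre-dose sample alone satisfies, for an outcome observable only on Day 14 or Day 28, and nothing elsewhere corrects it. If the set is the denominator, one pre-dose-only participant scales the rate by 5/6 in a 6-active cohort and by 7/8 in an 8-active cohort. With one positive, that means 16.7% instead of 20.0%, or 12.5% instead of 14.3%. Pooled over 34 active the change is negligible. It is zero if every dosed participant has a post-dose result.

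These sizes rest on assumed counts of positives and of pre-dose-only participants. The documents do not support a claim that missing post-dose results are scored negative or that pre-dose reactivity is scored positive. The handling of pre-dose reactivity is a secondary clarification. No power or error rate is affected.

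**What to change.** In protocol 8.7.1.5, the matching synopsis text and SAP Section 6, define the Immunogenicity Set as dosed participants with at least one post-dose (Day 14 or Day 28) ADA result.

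Do not make a Day 1 result a condition of membership, because that would discard valid post-dose results from anyone whose pre-dose sample is missing. Instead, add a short immunogenicity paragraph to the SAP that:

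- uses the Day 1 sample to classify ADA as pre-existing or new after dosing;
- shows baseline-positive and baseline-missing participants separately, by treatment group;
- reports the number dosed but without a post-dose ADA result;
- applies a titre-rise criterion only if the assay yields titres, which the documents do not describe.

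The cost is a few lines of text and possibly one or two fewer participants in the set. The wording should be settled before ADA results are available. Protocol 3.1 defers the ADA analysis until the method is established.

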7.1. General Statistical Consideration

If no other specified, SAS® (Version 9.4 or above) statistical software will be used for all statistical calculation and all analyses of safety part.

All summaries will be provided by treatment group for both study parts. Continuous variables will be summarized using descriptive statistics including number of observations (n), mean, standard deviation, median (med), minimum (min) and maximum (max). Categorical variables will be summarized using frequency and percentages.

For laboratory examination, keep 2 decimal places for mean, minimum, median, and maximum, 3 decimals for standard deviation. For percentage, keep 1 decimal place.

If no other specified, baseline of safety analysis is defined as the last effective assessment record before first treatment dosing.

7.2. Data Handling

7.2.1. Missing Data

Data evaluation will be based on the data collected by CRF without any imputation for safety part. If the categorical data is missing, it can be recorded as “missing” or “unknow”.

The missing date of AE will be imputed as follows. The imputation of missing date of AE is only used to classify AEs, and the original missing date record will still be presented when generating the listing of AE related data.

- If the start date of AE was missing
 - 1) If year and month were known and earlier than that of the first treatment dose, then impute with the last day of the known month.
 - 2) If the year and month were known as same as that of the first treatment dose, then impute the start date with the date of first treatment dosing (date in form of “XXX(Day)XXX(Month)”).
 - 3) If year and month were known and later than that of the first treatment dosing, then impute with the first day of the known month.
 - 4) If year only was known and earlier than that of the first treatment dosing, then impute date with “31Dec”.
 - 5) If year only was known and equal to that of the first treatment dosing, then impute the start date of AE as the first treatment dosing date (date in form of “XXX(Day)XXX(Month)”).
 - 6) If year only was known and later than that of the first treatment dosing, then impute with “1st JAN”.
 - 7) If year, month and day were all missing, use the first treatment dosing date as the start date of AE.
 - 8) Other conditions will be regarded as missing.
- If the end data of AE was missing
 - 1) If year and month were known, then impute with the last day of the known month.
 - 2) If year only was known, then impute with “31Dec”.
 - 3) If the start date was later than the end date after imputation, then use the start date directly as the end date.
 - 4) Other condition will be regarded as missing.

7.2.2. Derivation and Transformation on Data

Apart from the calculation of study endpoints mentioned in section 4, which are based on data collected via CRF, no derivation or transformation will be done for data. Outliers will be reported to data management function as data issue to be resolved or confirmed before database lock. No other special data handling will be done.

7.2.3. Handling PK data

For PK data handling, please refer to separate PK statistical analysis plan.

7.3. Study Subjects

7.3.1. Subjects Disposition

The frequency counts of subjects who signed the informed consent will be calculated, distinguishing those screen failures. Listing will be provided for subjects who were failed to screen with detail reasons.

Based on all subjects receiving randomization, the frequency counts and percentage of subjects who dosed, completed the study and withdrew early, as well as the frequency counts and percentage of subjects who withdrew early for various reasons, will be calculated and summarized.

Based on full analysis set, the frequency counts and percentage of subjects included in the full analysis set, safety analysis set will be calculated and summarized.

7.3.2. Protocol Deviations

Based on full analysis set, by-subject listing of all protocol deviation will be produced.

7.3.3. Demographics and Baseline Characteristics

All demographics and baseline characteristics analysis will be performed based on the full analysis set.

Descriptive statistical summary will be performed by treatment group on demographic data collected including age (in years, at time of signing informed consent), gender, race, ethnicity, height, weight, BMI, and smoking history.

Listing by subjects will be produced regarding to baseline demographic information collected.

Medical history collected will be coded by MedDRA (version refer to DMP).

Listing will be produced by subject for recording medical history, start data, end data of treatment, and current medication.

7.3.4. Prior/Concomitant Medication and Procedures

Analysis will be performed based on safety analysis set.

Prior/concomitant medications will be coded using the latest available WHO Drug Reference Dictionary (version refer to DMP).

All prior/concomitant medication data will be provided in listing by subject in detail, as well as prior/concomitant procedure.

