6.2. CONCOMITANT MEDICATIONS

Unless medication is necessary for safety reasons and approved by the Sponsor and the Investigator, participants must abstain from taking any prescription or non-prescription drugs, within 14 days or 5 times the half-life (whichever is longer) prior to the first dose of IP until completion of the study.

During the entire study period, participants must adhere to the following prohibitions:

- Able to abstain from the use of nicotine/tobacco containing products during the study.
- Able to abstain from the consumption of alcohol and any alcohol-containing products from 48 hours before dosing to the end of the study.
- Able to abstain from the consumption of coffee and any caffeine-containing products from 48 hours before dosing to the end of study.

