8.7.6. Concomitant Medications/Therapies

All prior and concomitant medications recorded in the case report form will be coded to all matching Anatomic Therapeutic Classification codes using the most recent version of the WHO Drug Dictionary. Descriptive summaries will be prepared using the coded term. All concomitant medications recorded in the case report form will be listed.

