7.4.6. Vital Signs

Vital signs results of each visit and their changes from baseline will be calculated and summarized by treatment group.

Listing by subject will be provided for all vital signs results. Abnormal with clinical significance results of vital signs will be provided by listing separately.

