7.4.7. Spirometry Assessment

Spirometry results of each visit and their changes from baseline will be calculated and summarized by treatment group.

Listing by subject will be provided for all spirometry assessment results. Abnormal with clinical significance results of spirometry assessment will be provided by listing separately.

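### The SAP lists concomitant medications but omits the descriptive summary the protocol requires, so treatment given for adverse events is tabulated by arm nowhere; spirometry also lacks a worst post-dose value

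*SAP*

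**What the plan says.** On medications, protocol 8.7.6 requires coding, then a summary ("Descriptive summaries will be prepared using the coded term"), then a listing. SAP 7.3.4 names the safety set as the population and keeps the coding, but the only output it specifies is "All prior/concomitant medication data will be provided in listing by subject in detail", with procedures handled likewise.

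On drug use during the study, protocol 6.2 requires abstinence from prescription and non-prescription drugs, with an exception that opens "Unless medication is necessary for safety reasons and approved by the Sponsor and the Investigator". Protocol 9.2.4 records for every adverse event whether medication or another treatment was given.

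On the measurements, SAP 7.4.7 says "Spirometry results of each visit and their changes from baseline will be calculated and summarized by treatment group", and SAP 7.4.6 has the same rule for vital signs: "Vital signs results of each visit and their changes from baseline will be calculated and summarized by treatment group". SAP 7.2.1 adds "Data evaluation will be based on the data collected by CRF without any imputation for safety part". SAP 7.2.2 says that, apart from calculating the endpoints in section 4, "no derivation or transformation will be done for data". The assessment schedules in both parts put spirometry at 5, 15, 30 and 60 minutes after dosing.

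**The concern.** The SAP should carry out what the protocol promises or explain why it does not. Here a promised table disappears without comment. In a placebo-controlled tolerability study, use of medication for events, by dose and placebo, is part of the safety picture. The protocol restricts other drugs and collects the treatment given for each event, so the information will exist, but no table presents it.

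Spirometry change is a primary outcome measure, included to detect acute bronchospasm. Such an effect may be brief, whether it resolves by itself or after treatment. A summary described only by visit may show the fall at one reading and normal means afterwards. If just one value per visit is used, it may not show the fall at all. What is at stake is how easily a reader of the report can see an acute reaction and its treatment by arm.

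**Working it through.** **Step 1. Protocol against SAP.**

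| Output for medications | Protocol 8.7.6 | SAP 7.3.4 |
|---|---|---|
| Coding | yes | yes |
| Descriptive summary | yes | not specified |
| By-participant listing | yes | yes |

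**Step 2. Does another clause supply the summary?**
- SAP 7.1 says that summaries are by treatment group. That sets the format of tables specified elsewhere and creates none.
- SAP 7.3.3 asks for a summary and, separately, a listing of demographics. The SAP therefore treats the two as different outputs, and a listing in 7.3.4 cannot be read as including a summary.
- Protocol 8.7 allows data in general to be listed, summarised or both. The specific rule in 8.7.6 asks for both.
- SAP 7.4.2 specifies nine adverse-event tables: overall, by class and term, serious, related, three on early discontinuation, and two by worst severity. None is by treatment given.

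**Step 3. Can the table be built from what is collected?** Protocol 7.7 and SAP 4.3.4 list medication name, dose, route, indication, start date and stop date. Start date and indication identify drugs begun on or after the first-dose date to treat an event. No new data are needed. Clock times are not listed for medications.

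**Step 4. Illustration for spirometry.** Group sizes come from protocol 8.4: 3 x (6 + 2) + 2 x (8 + 2) = 24 + 20 = 44, which reproduces the planned total and gives n = 6 active per Part A cohort and n = 8 per Part B cohort. The documents give no size or rate of bronchospasm. I therefore assume that one active participant falls by F points of FEV1 % predicted at 5 minutes, that the others do not change, and that a share r of the fall has reversed by a later reading.

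Mean change at a reading = -F(1 - r)/n.

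| n | F | r = 0 | r = 0.5 | r = 1 |
|---|---|---|---|---|
| 6 | 10 | -1.67 | -0.83 | 0 |
| 6 | 20 | -3.33 | -1.67 | 0 |
| 6 | 30 | -5.00 | -2.50 | 0 |
| 8 | 10 | -1.25 | -0.62 | 0 |
| 8 | 20 | -2.50 | -1.25 | 0 |
| 8 | 30 | -3.75 | -1.88 | 0 |

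**Step 5. Which summary keeps the fall?** Take F = 20, n = 6 and full reversal by 15 minutes.
- As recorded at 15, 30 and 60 minutes: 0/6 = 0.
- Leaving out the treated participant's later readings: 0/5 = 0, the same answer with the reactor removed.
- Each participant's worst change over the four readings: (-20 + 0 + 0 + 0 + 0 + 0)/6 = -3.3, with a minimum of -20, whatever r is and whether or not a drug was given.

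Only the last recovers the signal, and it needs no medication times.

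**The case against.** The case on the other side is substantial. This is a descriptive study with cohorts of 8 or 10, where listings can be read person by person. Summarising safety data as recorded is a legitimate choice. A fall would not vanish: SAP 7.1 requires the minimum, so a 20-point fall appears at 5 minutes if that reading is summarised. SAP 7.4.7 lists all spirometry results and separately lists the clinically significant abnormal ones. A clinically significant event becomes an adverse event and is tabulated by arm, relatedness and worst severity. All of this stands.

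Three stronger readings are therefore not supported.
- A reader might infer that treated reactions are lost or will pass for recovery. Later means can return to zero, but the event remains in the outputs just named, and nothing in the documents says how often or how fast treatment would act.
- A reader might infer that the missing table amounts to a table of treatment for adverse effects. It does not: the protocol's summary also covers prior medication, and inclusion criterion 6 accepts hormonal contraceptives during the study.
- A reader might infer that post-medication readings should be flagged and the summaries run with and without them. Step 5 shows that exclusion recovers nothing and removes the participant of interest. It would also need clock times that the documents do not list for medications.

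The objection does not reach two points. The SAP departs from protocol 8.7.6 without giving a reason, and listings are not the summary the protocol promised. The minimum at 5 minutes helps only if that reading is summarised, and SAP 7.4.7 does not say that it is.

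**Conclusion.** The point holds in a limited form. SAP 7.3.4 conflicts with protocol 8.7.6 on the medication summary, and treatment given for events is tabulated by arm nowhere. This follows from the text and rests on no assumption. The spirometry part is narrower: SAP 7.4.7 does not specify how the four post-dose readings enter the summary and gives no worst-value output, although the outcome is meant to detect an acute effect.

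The conflict bears on how safety data are displayed. It does not affect what is collected or how events are detected. The shifts of -3.3 points (n = 6) and -2.5 points (n = 8) are illustrations. They assume a single 20-point fall and no change in anyone else; for falls of 10 to 30 points the ranges are -1.67 to -5.00 and -1.25 to -3.75.

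**What to change.** **SAP 7.3.4.** Restore the descriptive summary of coded prior and concomitant medications by treatment group. Show separately the drugs started on or after the first dose to treat an adverse event. Keep the listing.

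**SAP 7.4.7.** Keep the as-recorded summaries. Add, by treatment group, each participant's worst post-dose change from baseline across the 5, 15, 30 and 60 minute readings. Part B repeats these readings on each dosing day, so state whether the worst value is taken per day, over all days, or both. Name the new variable in SAP 7.2.2 so that it is clearly allowed as an endpoint calculation.

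**Cost.** One or two extra descriptive tables and a few lines of SAP text, with no new data and no change to how participants are treated. One caution: the lowest of several readings tends to lie below baseline from measurement variation alone, so the worst-change table should be read against placebo. Placebo numbers are small: 2 per cohort, or 3 x 2 = 6 in Part A and 2 x 2 = 4 in Part B if combined.
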